#### 8.3 Primary Efficacy Endpoint(s) and Analyses

## 8.3.1 Primary Efficacy Endpoint

#### Spleen Volume Reduction ≥ 35% at Week 24 (SVR35W24) per IWG Criteria

SVR35W24 rate is defined as the proportion of subjects who achieved at least 35% reduction from baseline spleen volume at Week 24. The analysis window for Week 24 is defined as Day 127 to Day 211 per study activity schedule. Data after the start of post-study treatment or disease progression (relapse and progressive disease) will be excluded from the analyses. Subjects who do not have percent change from baseline (missing baseline or missing post-baseline) of spleen volume in the analysis window will be considered as non-responders.

Primary analysis population for SVR35W24 is the Full Analysis Set (see Section 4.0 for the definition of Full Analysis Set).

# 8.3.2 Main Analysis of Primary Efficacy Endpoint

[figure not shown]
The SVR35W24 rate will be estimated, and the corresponding 95% confidence interval (Cl) will be provided using the Clopper-Person method.

# 8.4 Secondary Efficacy Analyses

#### 8.4.1 Secondary Efficacy Endpoints

#### 8.4.1.1 TSS Reduction $\geq$ 50% at Week 24 (TSS50W24)

TSS50W24 rate is defined as the proportion of subjects who achieved at least 50% reduction from baseline in TSS at Week 24. TSS score at Week 24 is defined as the average of the daily scores from a 7-day period closest to Week 24 nominal period. The Week 24 nominal period is from Day 163 to Day 169 for subjects enrolled before protocol amendment 8 and from Day 162 to Day 168 for subjects enrolled after protocol amendment 7. The detail of finding the 7-day period closest to the Week 24 nominal period from MFSAF data is as follows. Also refer to Appendix C for more details.

- 1. Step 1: Search TSS 7-day period data in Week 24 nominal period, Day 162-168 (after protocol amendment 7) or Day 163-169 (prior to protocol amendment 8).
- 2. Step 2: If Step 1 data are not available, extend the Week 24 nominal period in increments of ± 1 day (e.g., for subjects enrolled after protocol Amendment 7: Day 163-169 (+1 day expansion), Day 161-167 (-1 day expansion))
- 3. Repeat step 2 in increments of  $\pm 1$  day until  $\pm 7$  days from Week 24 nominal period if data from previous step are not available
- 4. The final TSS at Week-24 is the average of 7-day period closest to the Week 24 nominal period. The following convention is applied to the situation when a pair of 7-day period data has the same distance to Week 24 nominal period: select the 7-day period data which is before Week 24 nominal period.

[figure not shown]
Daily TSS will be considered as missing if not all responses for 7 items are provided. The worst (highest) daily TSS score will be considered the daily TSS for a day when multiple responses were reported on the same day. At least 4 days of scores in the 7-day period of Week 24 Visit are required to calculate the TSS score for Week 24. If a subject does not have at least 4 days of scores in the 7-day period of Week 24 Visit, the subject will not have a TSS score at Week 24. TSS scores obtained after disease progression or start of post-study treatment will not be included in the analysis.

Primary analysis population for TSS50W24 is Full Analysis Set. Subjects with missing percent change in TSS at Week 24 (e.g., zero TSS at baseline, or missing either baseline or post-baseline) are considered as non-responders of TSS50W24.

#### 8.4.1.2 Anemia Response

Anemia response rate is defined as the proportion of subjects who achieved anemia response.

Baseline hemoglobin mentioned below is defined in Section 7.2.2. The transfusion dependency status (transfusion independent and transfusion dependent) mentioned below

are based on investigators reporting in the Study Cancer History Form according PRBC transfusion events ( $\geq 6$  units within 12 weeks and  $\geq 1$  unit within 28 days) prior to the start of study treatment.

For a subject who is transfusion independent (TI) at baseline with hemoglobin value < 10 g/dL, the subject will be considered as achieving anemia response if the post baseline hemoglobin level increases by  $\ge 2 \text{ g/dL}$  from baseline without receiving PRBC transfusion (for any reason) within 2 weeks and without any erythropoietin, erythropoietin mimetics within the last 4 weeks prior to the increase in hemoglobin level by  $\ge 2 \text{g/dL}$  was observed. Hemoglobin values after 30 days post last date of study treatment, the start of post-study treatment or disease progression whichever is earlier will not be considered in the analysis of anemia response.

For a subject who is transfusion dependent (TD) at baseline, anemia response is defined as a period of at least 12 consecutive weeks without PRBC transfusion after the first dose of study drug and on or prior to 30 days post last dose of study drug, the start of post-study treatment, disease progression or death, whichever occurs earlier.

[figure not shown]
Subjects who are baseline transfusion independent with baseline hemoglobin of  $\geq 10$  g/dL will not be included in the analysis since these subjects are not evaluable for anemia response.

Anemia response rate will also be summarized for all subjects who are evaluable for anemia response in the Full Analysis Set and by transfusion dependency status at baseline.

Missing post-baseline anemia response in Full Analysis Set applicable to evaluation of anemia response are considered as non-responders of anemia response.

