Navitoclax accelerates apoptosis of circulating mature platelets whether endogenous or transfused. This mechanism of toxicity differs from the thrombocytopenia caused by ruxolitinib and other conventional chemotherapy (i.e., toxicity to platelet progenitors in the bone marrow) and should, therefore, be managed according to the guidelines below and presented in detail in the toxicity management section of the protocol and Appendix I. Decisions regarding continued dosing, including the navitoclax or ruxolitinib (if applicable) dose level to be administered, for individual subjects will be medically managed by the Investigator in consultation with the AbbVie TA MD/SD.

Dose Adjustment Guidelines for Thrombocytopenia:

See Appendix I for comprehensive guidelines.

Criteria for Evaluation:

Efficacy:

To determine initial disease status, MRI/CT, bone marrow biopsy and aspirate will be obtained at Screening for all subjects. The local bone marrow evaluation will include staining for fibrosis and cytogenetics. To assess for efficacy, bone marrow biopsy, aspirate, MRI/CT, MFSAF and laboratory tests will be performed at designated timepoints throughout the study until disease progression is documented.

Efficacy will be assessed based on modified International Working Group-Myeloproliferative Neoplasms Research and European LeukemiaNet (IWG-MRT/ELN).

Transfusion requirements must be documented during the time period of 12 weeks before the start of navitoclax on Day 1.

Pharmacokinetic:

Pharmacokinetic samples for navitoclax (all cohorts) and ruxolitinib (1a, 1b, and 3) will be collected at designated time points throughout the study.

Biomarkers and Translational Research:

Exploratory research may be conducted to identify biomarkers predictive of navitoclax activity. Peripheral blood and bone marrow samples will be obtained at study specified time points. Biomarkers (e.g., but not limited to: allelic burden, mutational status, BCL-2 family profiling, inflammatory cytokine reduction) may be assessed to compare subject responses in order to identify markers that may be predictive of navitoclax activity alone or in combination with ruxolitinib.

Safety:

Adverse events (AEs), laboratory values, physical examinations, vital signs, and any additional 12-lead electrocardiogram (ECG) performed as clinically indicated will be assessed.

Statistical Methods:

Primary Efficacy Endpoint:

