During treatment, all assessments must be performed on the day of the specified visit unless a time window is specified in the schedule of assessments (Appendix C). Refer to Section 3.6 for study visit modifications.

Subjects will continue their treatment until end of clinical benefit, unacceptable toxicity or subject meets other protocol criteria for discontinuation (whichever occurs first). All subjects will have a TCV performed when treatment is discontinued.

Response and progression will be assessed by the Investigator based on the modified International Working Group-Myeloproliferative Neoplasms Research and European Leukemia Net (IWG-MRT/ELN) and as noted in Appendix E.²⁴ Spleen volume will be assessed by an independent central review and interpretations will be transmitted to investigators, as available, and will be utilized in determining response and progression. The evaluation of fibrosis grading and reticulin staining grading may be assessed independently by a central pathologist. Independent interpretations of bone marrow samples are not planned to be transmitted to investigators. Details regarding the determination of clinical response and disease progression are provided in Appendix E.

Follow-Up

Safety Follow-Up: All subjects will have one Safety Follow-up visit approximately 30 days following TCV.

Post-Treatment Follow-Up: For subjects who discontinue study treatment for reasons other than disease progression, a Post-Treatment Follow-up visit will be performed approximately 12 weeks following TCV, then every 12 weeks thereafter to assess disease

status until criteria are met for discontinuation from study (e.g., disease progression, initiation of post-treatment cancer therapy, or subject refusal of post-treatment follow-up visits).

Once disease progression is confirmed or the subject begins a post-study treatment for MF other than the continuation of ruxolitinib (Cohorts 1a, 1b or 3), the subject will enter the Survival Follow-up phase.

Survival Follow-Up: Survival Follow-up will then be performed approximately every 6 months for up to 5 years after TCV (provided informed consent has not been withdrawn for collection of such information). Survival information (e.g., date and cause of death, details of post-treatment cancer therapies including response and progression) may be collected via telephone calls (e.g., to subject or family member), clinic visits, and/or public database searches.

5.2 **Selection of Study Population**

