Appendix E. Modified IWG-MRT/ELN Response Criteria for Myelofibrosis

Table 9. Summary of Response Criteria

		nents (for all response categori							
Response	for	$r \ge 12$ wk to qualify as a respon	ise)						
Category	Bone Marrow	Peripheral Blood	Clinical						
Complete Remission (CR)	 Age-adjusted normocellularity < 5% blasts Grade ≤ 1 MF (Appendix F) 	 Hgb ≥ 10g/dL Neutrophils ≥ 1 × 10⁹/L Platelets ≥ 100 × 10⁹/L < 2% immature myeloid cells 	 Resolution of disease symptoms Spleen/Liver not palpable No evidence of EMH 						
Partial Remission (PR)	Not Applicable	 Hgb ≥ 10 g/dL Neutrophils ≥ 1 × 10⁹/L Platelets ≥ 100 × 10⁹/L < 2% immature myeloid cells 	 Resolution of disease symptoms Spleen/Liver not palpable No evidence of EMH 						
		OR							
	 Age-adjusted normocellularity < 5% blasts Grade ≤ 1 MF (Appendix F) 	 Hgb ≥ 8.5 g/dL Neutrophils ≥ 1 × 10⁹/L Platelets ≥ 50 × 10⁹/L < 2% immature myeloid cells 	 Resolution of disease symptoms Spleen/Liver not palpable No evidence of EMH 						
Clinical Improvement		pleen or symptom response with thrombocytopenia or neutropeni							
Anemia Response	•	eline Hgb < 10 g/dL): Hgb incre ning transfusion independent**	ase $\geq 2 \text{ g/dL}$						
Spleen Response	A baseline splenomegaly that is palpable at $5-10$ cm below the LCM, becomes not palpable*** A baseline splenomegaly that is palpable at >10 cm below the LCM, decreases by $\geq 50\%$ *** MRI/CT showing $\geq 35\%$ SVR								
Symptoms Response	≥ 50% reduction in MF-SAF T	TSS							
Stable Disease	Belonging to none of the above	e response categories							

EMH = extramedullary hematopoiesis; LCM = left costal margin

^{*} Increase in severity of anemia constitutes the occurrence of new transfusion dependency or a ≥ 2 g/dL decrease in Hgb from pretreatment baseline that lasts for ≥ 12 weeks. Increase in severity of thrombocytopenia or neutropenia is defined as a 2-grade decline, from pretreatment baseline, in platelet count or ANC. In addition, assignment to Clinical Improvement requires a minimum platelet count of ≥ 25 × 10⁹/L and ANC ≥ 0.5 × 10⁹/L.

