^{**} Transfusion dependency before study enrollment is defined as transfusions of at least 6 units of packed red blood cells (PRBC), in the 12 weeks prior to study enrollment. In addition, the most recent transfusion episode must have occurred in the 28 days prior to study enrollment. Response in transfusion-dependent patients requires absence of any PRBC transfusions during any consecutive "rolling" 12-week interval during the treatment phase.

^{***} Requires confirmation by MRI/CT with a \geq 35% SVR.

[figure not shown]

Table 10. Summary of Cytogenetic Remission

Cytogenetic Remission Category	Cytogenetic Remission Requirements At least 10 metaphases must be analyzed
	Requires confirmation by repeat testing within 6 months
Complete Cytogenetic Remission	Eradication of a preexisting abnormality
Partial Cytogenetic Remission	\geq 50% reduction in abnormal metaphases (to qualify for PR: must have \geq 10 abnormal metaphases at baseline)

Table 11. Summary of Molecular Remission

Molecular Remission	Molecular Remission Requirements		
Category	Must be analyzed in peripheral blood granulocytes		
	Requires confirmation by repeat testing within 6 months		
Complete Molecular Remission	Eradication of a pre-existing abnormality		
Partial Molecular Remission	\geq 50% decrease in allele burden (to qualify for PR: must have \geq 20% mutant allele burden at baseling		

[figure not shown]

Table 12. Summary of Progression/Relapse Criteria

Progression/Relapse Category	Progression/Relapse Criteria		
Progressive Disease	At least 1 of the following:		
	• Appearance of a new splenomegaly that is palpable at least 5 cm below the left costal margin (LCM)*		
	• A \geq 100% increase in palpable distance below LCM, for baseline splenomegaly of 5 – 10 cm*		
	• A 50% increase in palpable distance below LCM, for baseline splenomegaly of > 10 cm*		
	• MRI/CT showing a \geq 25% increase in spleen volume from baseline		
	• Leukemic transformation confirmed by a bone marrow blast count of ≥ 20%		
	• A peripheral blood blast content of $\geq 20\%$ associated with an absolute blast count of $\geq 1 \times 10^9/L$ that lasts for at least 2 weeks		
Relapse	At least 1 of the following:		
	No longer meeting criteria for at least Clinical Improvement after achieving Complete Response, Partial Response or Clinical Improvement		
	• Loss of anemia response persisting for ≥ 1 month		
	• Loss of spleen response persisting for ≥ 1 month		

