# 8.0 Efficacy Analyses

#### 8.1 General Considerations

The primary analysis population for primary endpoint is the Full Analysis Set. Unless otherwise specified, the secondary efficacy endpoints and exploratory efficacy endpoints will be analyzed in Full Analysis Set.

All efficacy results will be presented by cohort unless stated otherwise. For all analyses, unless otherwise specified, data collected after the cutoff date will be excluded from statistical analysis. All spleen volume related endpoints described in Section 3.0 will be based on the assessments from the central review of the radiographic images by an Independent Review Committee (IRC) as described in the protocol.

abbyie Navitoclax/ABT-263

Navitoclax/ABT-263 M16-109 – Statistical Analysis Plan Version 4.0 – 31 January 2023

All response rates and the corresponding 95% confidence interval (Cl) using the Clopper-Pearson method will be provided.

For the analyses of all time-to-event endpoints, survivorship functions will be estimated using Kaplan-Meier product-limit methodology. If reached, median time-to-event and its 95% CI will be presented.

For the analyses of all continuous endpoints, such as change from baseline in score, the scores will be summarized with baseline mean, visit mean, mean change from baseline, mean percentage change from baseline, standard deviation, and the corresponding 95% CIs.

Baseline measurement related to each efficacy endpoint for analysis has been described in Section 7.0.

[figure not shown]
The post-study treatment refers to Post Study Drug Systemic Therapies for Myelofibrosis, Post Study Drug Radiation Therapy and Post Study Drug Transplant. The disease progression (DP) refers to relapse or progressive disease in the Disease Response Assessment Form.

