#### 8.5.1.7 Duration of Anemia Response

Duration of anemia response will be summarized by baseline transfusion status.

For subjects who were transfusion independent at baseline and achieved anemia response, the evaluation period for duration of anemia response is from achieving anemia response to 30 days after last dose of study treatment. Duration of anemia response is defined as number of days from the first date of achieving anemia response described in Table 6 to the date of loss anemia response as described in Table 7.

Table 6. Date of First Anemia Response for Duration of Anemia Response

Transfusion Status at baseline	Date of First Response
TI	On the first date observing hemoglobin level increase by $\geq 2$ g/dL from baseline without receiving PRBC transfusion within the last 2 weeks or any erythropoietin, erythropoietin mimetics within 4 weeks prior to the increased hemoglobin level
TD	On the first date observing no PRBC transfusion for at least 12 weeks

Table 7. Event and Censoring Condition for Duration of Anemia Response

[figure not shown]
Transfusion Status at baseline	Event/Censor	Date of Event/Censor
TI	Event: 1) decrease in hemoglobin level by 2 g/dL or more from the hemoglobin level at the first occurrence of achieving anemia response, or 2) need for PRBC transfusion before disease progression for the bleeding event* which was unrelated to navitoclax/ruxolitinib or 3) use of any erythropoietin, erythropoietin mimetics within 30 days of last dose of study drug	Earliest date of events
	Censor: if no above-mentioned events observed within 30 days of last dose of study drug	The last date of hemoglobin assessment after achieving anemia response, 30 days post last dose of study treatment, start of post-study treatment, disease progression, or death, whichever is earlier.  Date of achieving anemia response will be the censor date if no hemoglobin assessment is obtained after achieving anemia response.

\* Bleeding event is defined as a treatment emergent hemorrhage event from narrow search of Standardized MedDRA Queries (SMQ). PRBC occurring between the start of bleeding event and end/ongoing will be considered as need for PRBC transfusion for bleeding.

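### For transfusion-independent subjects the SAP scores anemia response on one hemoglobin value, although the protocol's only definition of this secondary endpoint requires at least 12 weeks

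*SAP*

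**What the plan says.** **SAP 8.4.1.2.** For a transfusion-independent (TI) subject with baseline hemoglobin below 10 g/dL, "the subject will be considered as achieving anemia response if the post baseline hemoglobin level increases by" 2 g/dL or more. There must be no PRBC transfusion in the 2 weeks before the value and no erythropoietin or mimetic in the 4 weeks before it. Values after progression, after post-study treatment or more than 30 days after the last dose are excluded. No persistence or confirmation is asked for. A transfusion-dependent (TD) subject needs at least 12 consecutive weeks without PRBC. The rate is given for all evaluable subjects and by baseline transfusion status.

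**SAP 8.5.1.7, Tables 6 and 7.** TI response is dated to the first day on which the rise is seen. A responder with no later hemoglobin value is censored on that same day.

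**Protocol.** Sections 5.3.3, 8.2.2 and 8.3.1 name anemia response without criteria. The Synopsis says "Efficacy will be assessed based on modified International Working Group-Myeloproliferative Neoplasms Research and European LeukemiaNet (IWG-MRT/ELN". Section 5.1 adds: "Details regarding the determination of clinical response and disease progression are provided in Appendix E". In Appendix E, the Table 9 heading is broken in the extracted text, but its scope ("nents (for all response categori") and its duration of at least 12 weeks ("wk to qualify as a respon") can be read. The anemia row, with the same thresholds of below 10 g/dL and +2 g/dL, stands under that heading.

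**SAP Appendix B, Table B-1** repeats the rows of Table 9 without the 12-week condition.

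**The concern.** The SAP takes the thresholds of Table 9 but not its duration. A TI subject whose hemoglobin is high at one visit and back at baseline at the next counts as a responder. Under Appendix E the same subject does not.

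Two things are at stake. The TI rate can include chance fluctuation, and TI subjects are measured many times. The all-evaluable rate also combines two time standards: one value for TI subjects, 12 weeks for TD subjects. A reader who takes the result as the Appendix E response would be misled, and nothing in the SAP warns of this.

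**Working it through.** **1. Is one value really enough?** The SAP does not use the word single. The reading follows from the absence of any duration in 8.4.1.2, from the Table 6 response date, and from the Table 7 rule that censors a responder with no later value on the response date. That subject has one qualifying value and remains a responder.

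**2. Does the protocol set another time rule for anemia?** No. Where it wants response at any time it says so, as for exploratory SVR35 and TSS reduction in 5.3.3. For anemia response it gives none, so Table 9 is the only source.

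**3. Size.** The plan states no expected anemia response rate, so there is no figure to reproduce. The within-subject SD of hemoglobin is an assumption, taken as 0.5, 0.7 and 1.0 g/dL.

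Inputs: ten scheduled post-baseline hematology visits to Week 24 (Weeks 1, 2, 3, 4, 6, 8, 12, 16, 20, 24), then every 12 weeks; one baseline value; normal errors; weekly autocorrelation 0, 0.7 or 0.9.

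With independent errors, a change from baseline has SD equal to SD × √2, so the chance at one visit is 1 − Φ(2 / (SD × √2)):

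- SD 0.5: 1 − Φ(2.83) = 0.2%
- SD 0.7: 1 − Φ(2.02) = 2.2%
- SD 1.0: 1 − Φ(1.41) = 7.9%

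The visits share a baseline, so the chance of at least one such value was simulated (400,000 subjects per setting). The 12-week rule requires every scheduled value to be at +2 g/dL or more over at least 12 weeks. Ranges run over the three autocorrelations.

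| | SD 0.5 | SD 0.7 | SD 1.0 |
|---|---|---|---|
| No true change, one value, Week 24 | 0.3–1.9% | 3.8–12.8% | 15–34% |
| No true change, 12-week rule, Week 24 | under 0.01% | 0.09–0.15% | 0.9–1.3% |
| No true change, one value, Week 96 | 1.3–2.7% | 10.5–16.8% | 31–42% |
| No true change, 12-week rule, Week 96 | 0.1–0.2% | 1.5–2.2% | 7.9–9.9% |
| Mean fall of 0.5 g/dL, one value, Week 24 | 0.02–0.2% | 0.9–4% | 7–20% |
| True +2.5 g/dL from Week 4, 12-week rule, Week 24 | 57–69% | 48–60% | 41–52% |

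At SD 0.7 the single-value rule catches about 96% of the true +2.5 g/dL rises by Week 24. The 12-week rule misses 40% to 52% of them (100 − 60 and 100 − 48).

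**The case against.** **The link to Table 9 is indirect.** Protocol 5.3.3 attaches the modified IWG label to several exploratory endpoints but not to anemia response. It also uses that label for SVR35 at any time point, so the label alone does not always carry 12 weeks. Section 8.3 leaves details to the SAP. This softens the charge from error to undisclosed departure, but no further. The Synopsis and Section 5.1 send response to these criteria, no other definition exists, and the SAP itself uses the Table 9 thresholds.

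**The rates by transfusion status separate the two standards.** That is right, and a reader should not infer that the mixture is hidden. The separation does not correct the TI rate.

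**The false-response figures may be too high.** Protocol 5.6.3 names anemia among the main reasons for ruxolitinib dose reduction, so a mean fall in hemoglobin is plausible. An assumed fall of 0.5 g/dL cuts the figures substantially, as the table shows.

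**The 12-week rule loses true responders.** This stands, and it is why both rates are needed.

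**Two stronger readings are tempting.** The first is that an earlier SAP contained the 12 weeks and a later one removed them. The SAP version history records edits to anemia response in version 1.1 and in the version 3.0 draft, but does not show that. The second is that Table 7 censors the losses of chance responders as relapse. Relapse is recorded by investigators applying Appendix E, under which a chance rise shorter than 12 weeks was never a response that could be lost.

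**Conclusion.** The departure is real and does not depend on any assumed SD: Appendix E requires at least 12 weeks, while SAP 8.4.1.2 requires one value and does not say that it differs. The size is uncertain. By Week 24, with no mean change, one value scores about 0.3% to 34% of unchanged subjects as responders for an assumed SD of 0.5 to 1.0 g/dL, against at most about 1.3% under the 12-week rule. At the low end, or with a mean fall in hemoglobin, the effect can be negligible. These figures show direction and possible size; they are not estimates for this trial.

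A reader might infer that the trial's main conclusion is affected. It is not. The endpoint is secondary and reported as a rate with an exact interval and no test. The primary endpoint and the sample size do not use it. The change should still be made, because it is cheap and the name of the endpoint otherwise promises more than the rule delivers.

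One lesser point concerns only the exploratory duration endpoint. Protocol Table 12 and SAP Table B-4 list as relapse "Loss of anemia response persisting for" at least 1 month. SAP 8.1 says that disease progression "refers to relapse or progressive disease in the Disease Response Assessment Form", and the Table 7 censoring dates include "start of post-study treatment, disease progression, or death, whichever is earlier". A qualified responder's loss, if recorded as relapse, is therefore censored unless another Table 7 event occurs.

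**What to change.** - In SAP 8.4.1.2, define TI anemia response as a rise of at least 2 g/dL maintained for at least 12 weeks, with no PRBC, erythropoietin or mimetic in the interval and the existing look-backs at its start.
- State how 12 weeks is counted: either 84 days or more, as in SAP 8.5.1.6, or one written visit-window convention. The choice matters. After Week 24 the visit windows are ±4 days, so nominal visits 12 weeks apart can be 84 − 4 − 4 = 76 days apart.
- Fix one rule before analysis for an isolated value below +2 g/dL. In the simulation at SD 0.7, allowing one such dip raises the capture of true +2.5 g/dL rises by Week 24 from 48–60% to 67–69%, at a false rate of about 0.2–0.45%.
- Restore the 12-week heading in Table B-1, and date TI response in Table 6 to the start of the qualifying interval.
- Report the single-value rate beside the 12-week rate, labelled as not meeting the Appendix E duration condition.
- In Table 7, count a qualified responder's loss that is recorded as relapse as an event, not as a censoring.

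The cost is SAP wording and reprogramming of one derivation and its duration, from data already collected. The reported rate will fall. A rise that starts after Week 12 cannot qualify in a subject with only 24 weeks of follow-up. If every scheduled value must hold, stringency varies with visit spacing: a rise first seen at Week 1 needs eight consecutive values (Weeks 1 to 16), one first seen at Week 24 needs two.

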#### 7.2.2 Baseline Hemoglobin Laboratory Value

For hemoglobin laboratory test the baseline value will be defined as follows:

For subjects who received PRBC transfusion (for any reason) within 4 Weeks on or before the first date of study treatment, the baseline value is the minimum value observed before the transfusion, and the last non-missing value on or prior to the first date of study treatment.

For subjects who do not receive PRBC transfusion within 4 weeks on or before the first date of study treatment, the baseline value is the last observed value on or before the first date of study treatment.

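### Anemia response in transfusion-independent subjects uses a 4-week transfusion look-back at baseline but only 2 weeks after baseline, so hemoglobin measured 15 to 28 days after PRBC can count as a response

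*SAP*

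**What the plan says.** Anemia response is a secondary endpoint (SAP 3.2). For a transfusion-independent subject it is the difference between a post-baseline and a baseline hemoglobin, and each side has its own transfusion rule.

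- **Baseline (SAP 7.2.2).** For PRBC given "within 4 Weeks on or before the first date of study treatment, the baseline value is the minimum value observed before the transfusion". The sentence then names a second candidate, the latest hemoglobin available at first dose. The natural reading is that the lower of the two is used.
- **After baseline (SAP 8.4.1.2).** A rise of at least 2 g/dL qualifies if it occurs "without receiving PRBC transfusion (for any reason) within 2 weeks". For erythropoietic agents the same sentence looks back further: "erythropoietin mimetics within the last 4 weeks prior to the increase in hemoglobin level".
- **Date of first response (SAP 8.5.1.7, Table 6).** The same pair of windows is repeated: "without receiving PRBC transfusion within the last 2 weeks or any erythropoietin, erythropoietin mimetics within 4 weeks".
- **Who is independent.** Dependence requires "transfusions of at least 6 units of packed red blood cells (PRBC), in the 12 weeks prior to study enrollment" (protocol Appendix E) and a transfusion in the last 28 days. SAP 8.4.1.2 uses the same thresholds, as reported by the investigator before treatment. Everyone else is independent.
- **On-study transfusion.** Protocol 5.2.4 allows it as supportive care for every subject.

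SAP 8.4.1.2 has no confirmation or duration requirement for independent subjects. Protocol Appendix E, Table 9, carries a 12-week condition in its header; SAP Table B-1 does not.

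**The concern.** The two sides of one difference treat a recent transfusion differently, and both choices widen the difference. Blood given 20 days before first dose sends the baseline back to a pre-transfusion value. Blood given 20 days before an on-study measurement leaves that measurement eligible. The SAP gives no reason for using 4 weeks on one side and 2 on the other.

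The independent label does not prevent this, because it covers subjects who receive blood below the dependence threshold and it is not revised when transfusion increases on study. One value is enough to respond, so a temporary rise from donor blood can be scored as a drug effect.

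At stake is an upward bias in a reported secondary response rate. The study has no control group in which the same artefact would appear. The same date also starts the duration of anemia response, and under Table 7 PRBC ends that response only when tied to a bleeding event. A later transfusion for anemia does not by itself end it.

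**Working it through.** The documents give no expected rate, sample size or precision for anemia response, so there is no stated figure to reproduce.

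**1. The gap.** 28 − 14 = 14 days: a value taken 15 to 28 days after PRBC passes the post-baseline rule, although PRBC of that age triggers the baseline rule.

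**2. Where it falls.** Scheduled hematology (protocol Appendix C, Table 6) is on Days 8, 15, 22, 29, 43, 57, 85, 113, 141 and 169, then every 12 weeks. Subtracting 15 to 28 days, PRBC on Days 1–14 is in the gap at Day 29, Days 15–28 at Day 43, Days 29–42 at Day 57, and Days 57–70 at Day 85. Blood given before treatment can also qualify. PRBC 8 days before Day 1 triggers the baseline rule, yet is 8 + 7 = 15 days old at the Day 8 visit.

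**3. Direction.** Independent subjects are evaluable by baseline hemoglobin, so the denominator does not depend on the post-baseline window. Every value that passes a 4-week window also passes a 2-week window. The 2-week rate is therefore equal to or higher than the 4-week rate.

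**4. Who can be affected.** Take regular 2-unit transfusions, the last one d days before treatment.

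- Every 21 days: 4 episodes in 84 days, 8 units, last within 28 days. Dependent at every d.
- Every 28 days: 3 episodes, 6 units, last within 28 days. Dependent at every d.
- Every 35 days: d = 0–14 gives 3 episodes and 6 units, dependent. d = 15–28 gives 4 units, independent with the baseline rule triggered. d = 29–34 is independent, but the baseline rule is not triggered. So 14 of 35 phases (40%) combine both conditions.

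To stay at 5 units in 12 weeks, a subject transfused every 3 weeks averages at most 5/4 = 1.25 units per episode, and every 4 weeks 5/3 = 1.67.

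**5. Can +2 g/dL survive to days 15–28?** Assumptions not in the documents: r = 0.7 to 1.3 g/dL per unit, linear loss over L = 60 to 120 days, the subject's own hemoglobin unchanged. Units needed = 2 / [r(1 − day/L)], rounded up:

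| r | L | Day 15 | Day 21 | Day 28 |
|---|---|---|---|---|
| 0.7 | 60 | 4 | 5 | 6 |
| 0.7 | 120 | 4 | 4 | 4 |
| 1.0 | 60 | 3 | 4 | 4 |
| 1.0 | 120 | 3 | 3 | 3 |
| 1.3 | 60 | 3 | 3 | 3 |
| 1.3 | 120 | 2 | 2 | 3 |

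In the pre-treatment case of step 2, with a pre-transfusion value of 7.8 g/dL, 4 or 5 units give a response at Day 8 in every scenario. Three units do so when r is 1.0 or more.

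Under a stable transfusion need the route is narrower. If hemoglobin falls linearly back to its trough over 35 days, 19/35 = 54% of the rise remains at day 16. A 2 g/dL excess then needs an immediate rise of 2/0.54 = 3.7 g/dL, or 1.84 g/dL per unit from 2 units, above the assumed range.

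**6. Effect per false responder.** It adds 1/n to the independent-subject rate: 10.0, 5.0, 3.3 and 2.5 points at assumed n = 10, 20, 30 and 40. At n = 20, two false responders turn 0% (exact 95% CI 0 to 16.84) into 10.0% (1.23 to 31.70).

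**The case against.** The strongest reply is that 4 weeks is not a carry-over standard the SAP has adopted. SAP 7.2.2 keeps the latest value as a second candidate, so a post-transfusion value is not discarded, only passed over when higher. Protocol Appendix E sets no transfusion washout for a hemoglobin response, and the 4-week erythropoietin window concerns a different agent. A reader might infer that the SAP itself declares hemoglobin contaminated for 4 weeks; its text does not say so. This part of the reply stands. What remains is an unexplained difference between two rules for one endpoint.

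A second tempting inference is that a large share of values in regularly transfused subjects would be false responses. With a random phase, roughly 29–33% (6/21 to 7/21), 46–50% (13/28 to 14/28) and 40% (14/35) of measurements fall 15 to 28 days after the last transfusion for 3-, 4- and 5-week intervals. These shares describe time spent in the window, not responses. Subjects on regular 2-unit schedules at 3 or 4 weeks are dependent and are judged on 12 transfusion-free weeks instead. This limits the affected group, as steps 4 and 5 of the working show, but does not empty it: larger episodes, or transfusion that increases on study, remain.

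Third, the missing duration requirement matters more. The protocol's 12-week condition, if applied, would remove most short-lived rises. That is fair, but the SAP rule for independent subjects does not apply it, so it does not close the gap here.

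Finally, a lower baseline also brings more subjects below 10 g/dL into the denominator, and transfusion use is reported separately (SAP 8.5.1.6 and 9.2.5.3). Both points soften the consequence without changing which values qualify.

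**Conclusion.** The point holds in a limited form. The windows differ, no other SAP passage closes the 15-to-28-day gap, and for a given baseline the shorter post-baseline window can only leave the response rate unchanged or raise it.

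The size cannot be computed. The documents give no number of anemic transfusion-independent subjects, no on-study transfusion rate and no hemoglobin rise per unit. The illustrations rest on the stated assumptions about rise and loss; holding the subject's own hemoglobin constant favors carry-over. Under them, 2 to 4 units are needed at day 15 and 3 to 6 at day 28, so the route is mainly larger transfusion episodes, shortly before Day 1 or on study, or rising transfusion use.

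Severity is minor to moderate. The endpoint is secondary and is estimated with an exact interval and no formal test (protocol 8.3; SAP 8.4.2), so a reported rate may be too high but no error rate is breached.

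**What to change.** In SAP 8.4.1.2 and in Table 6 of SAP 8.5.1.7, change the PRBC window before the qualifying hemoglobin value from 2 weeks to 4 weeks, matching SAP 7.2.2. If the sponsor keeps 2 weeks, the SAP should give the reason for the difference and pre-specify the 4-week version as a sensitivity analysis for both the transfusion-independent rate and the overall anemia response rate.

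The cost is a wording change and reprogramming; transfusion history and status are already collected (protocol Appendix C, Table 6). The rate may be slightly lower. A true responder with an incidental transfusion may qualify only at the next clean scheduled visit. From Week 8 to Week 24 visits are 4 weeks apart, and after that 12 weeks apart, so the delay can exceed the 2 weeks added to the window, and an occasional true response may be missed. Reporting both windows would show how much this matters.
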